## 15.2 Populations to be analysed

The final analysis populations will be described in the Statistical Analysis Plan (SAP), which will be signed off before database lock.

#### 15.2.1 Intent-to treat (ITT) population

The ITT population will consist of all randomized patients in the groups to which they were randomly assigned, and who have taken at least one dose of study treatment.

#### 15.2.2 Adequate adherence (AA) population:

The AA population will be the same as the ITT population with the following patients excluded:

- Randomised patients not meeting the eligibility criteria
- Patients having missed 10 or more doses of their allocated treatment in the first 16 weeks of their treatment.

#### 15.2.3 Safety Population

The safety population will be defined as all patients who received any dose of study medication.

#### **15.3** Analysis of safety endpoints

The safety analysis population will be used for all safety analyses.

#### 15.3.1 ECG analysis

QT and QTc data will be analysed categorically based on the number and percentage of patients classified in each category by treatment group. QTc data will be presented for Friderica's corrections.

Post-baseline QT- and QTc-intervals will be classified into the following categories:

- QT/QTc<450 ms
- 450 ms <QT/QTc <480 ms
- 480 ms < QT/QTc < 500 ms
- QT/QTc > 500 ms

QTc-changes from baseline will be classified into the following categories:

- decrease (an increase < 0 ms)
- increase < 30 ms
- >30 ms and < 60 ms
- increase >60 ms

#### 15.3.2 Adverse Events

The incidence of treatment – emergent adverse events, defined as all AEs that occur after the administration of IMP, and their relatedness to experimental treatment will be summarised by treatment group, by system organ class and preferred term, maximum severity, and potential relationship to IMP, as well as TEAEs with an outcome of death, serious TEAEs, and discontinuations due to TEAEs.

Adverse events will be coded using the Medical Dictionary for Regulatory Activities (MedDRA) dictionary.

#### 15.3.3 Other safety variables

Binary and categorical variables will be tabulated by treatment arm. Continuous variables will be summarised with location (such as mean or median) and precision (such as standard error or interquartile range) summary estimates.

Patients with worsening condition from baseline on any variable will be described and tabulated. The following variables will be analysed:

- Laboratory Parameters: a list of safety laboratory parameters collected in the trial is described under section 11.3.
- Ophthalmologic Variables: Visual Acuity (Snellen) and Colour Vision (Ishihara) tests
- Physical Examination incl. neurological examination; esp. presence of Hunter score criteria
- Vital signs

## 15.4 Analysis of primary efficacy endpoint

The primary efficacy endpoint of this study will be change in mycobacterial load over time on treatment as quantified by time to positivity in BD MGIT 960® liquid culture and described by nonlinear mixed-effects methodology. All patients in the ITT analysis population will be included in this analysis

This endpoint will be analysed by non-linear mixed effects modelling.

## **15.5** Procedure for accounting for missing, unused and spurious data

Study data will, after being entered, be checked for consistency and completeness through programmed checks by the database, which will raise automatic queries. Further completeness and consistency checks will be performed by data management and any resulting queries will be sent through the database query system so as to leave an audit trail.

## 15.6 Procedure for reporting any deviations from the original statistical plan

Any deviations from the Statistical Analysis Plan will be reported and explained in the Clinical Study Report.

## **15.7** Timing of analyses

Analysis for the primary endpoints, and secondary endpoints unrelated to disease recurrence or relapse, will be performed after data are available (allowing for time for culture growth) after the last patient completed their WK16 (or otherwise last treatment) visit. A partial database lock will be performed for this purpose, with a final database lock at the end of study after all long-term outcome data are available.

# 16 DATA HANDLING AND QUALITY ASSURANCE

Protocol No: PanACEA - DECODE - 01/ LCB01-0371-20-2-02 Protocol Version No: V2.1, dated 08 September 2021

# 16.1 Data collection

The investigator agrees to maintain accurate source documentation and CRFs. For each patient screened, an electronic CRF (eCRF) will be completed, even if the patient drops out at any time point during the study. All eCRF information for the completed visits must be completed.

All applicable eCRF pages must be completed for each participant, who has received any dose of study drug and has completed the study.

For participants who are prematurely withdrawn, the visits up to withdrawal plus the withdrawal visit need to be completed.

In the case of necessary corrections, all changes will be effectuated such that the first version is still legible, and the change is initialled and dated by the correcting person. Each completed eCRF must be reviewed, signed and dated by the responsible Principal Investigator or the sub-investigator in a timely manner.

## **16.2 Source documents**

Source data are defined as all information in original records and certified copies of original records of clinical findings, observations, or other activities in a clinical trial necessary for the reconstruction and evaluation of the trial. Source documents will include, but are not limited to, progress notes, electronic data, screening logs and recorded data from automated instruments.

Study data will be collected and entered into the eCRF. Some data may still be captured entirely or partially on paper source documents and will manually be entered into an eCRF, including but not limited to:

- Informed Consents
- Chest X-ray images and reviews
- Sample collection data (will be on Lab Forms except for HIV and malaria test results)
- Safety and microbiology laboratory results and their review by the investigator.

All paper source documents and the electronic source documents pertaining to this trial will be maintained by the investigators. The investigator will be obliged to permit trial-related monitoring, audits, Independent Ethics Committee/Institutional Review Board (IEC/IRB) review and regulatory inspections, providing authorized persons direct access to source data/documents.

## **16.3 Study monitoring**

One or more study monitors will be assigned to the study. The monitor, as a representative of the Sponsor, has the obligation to follow the study closely. The monitor will visit the site at regular intervals and will be in contact by phone and written communication, as required.

Site investigators and designated study personnel will allow the study monitors to inspect study documents, pertinent hospital or clinic records as well as site facilities, as required. All aspects of

the study will be carefully monitored in order to ensure compliance with GCP and all applicable regulatory guidelines. The monitor will be responsible for verification of:

- adequacy of study personnel's qualifications as well as facilities
- informed consent procedures and patient eligibility
- the accuracy and completeness of the (e)CRF entries, source data and other trial-related records against each other
- appropriate study drug storage, usage and accountability
- appropriate adverse event reporting
- maintenance of the essential documents
- all other aspects of the trial relating to protection of the rights and well-being of patients, accuracy of trial data and adherence to the protocol, GCP and applicable regulatory requirements

Source data verification will be carried out according to the *monitoring plan*.

The sponsor will provide a framework for maintenance of quality in performance and reporting of laboratory procedures through the *laboratory monitoring plan*.

The study database will only be locked after the data have been monitored by the sponsor and all queries issued through data cleaning activities have been completed and resolutions documented.

## **16.4** Inspection of records

The investigator will allow the Sponsor, the Sponsor's Representative, Regulatory Agencies and Ethics Committees access to all study records, if requested. The investigator will promptly notify the sponsor of any audits scheduled by regulatory authorities or ethics committees and promptly forward copies of any audit reports received to the sponsor.

## **16.5 Records retention**

Essential documents should be retained until at least 2 years after the last approval of a marketing application in the International Conference on Harmonization (ICH) region and until there are no pending or contemplated marketing applications in an ICH region or at least 2 years have elapsed since the formal discontinuation of clinical development of the investigational product, or for not less than 10 years after trial completion, whichever is longer.

These documents should be retained for a longer period, however, if required by the applicable regulatory requirements or by an agreement with the sponsor. It is the responsibility of the sponsor to inform the investigator/institution as to when these documents no longer need to be retained.

# **16.6** Confidentiality of personal data

All patient records, lab specimen etc. will be identified in appropriate manner to maintain patients' confidentiality and will be kept in a secure storage area with limited access. Clinical data will not be released without the written agreement of the patient (or their legal guardian), except as necessary for monitoring and auditing by the sponsor or its representative, regulatory authorities or ethics committees.

For those participants who gave consent to store genetic samples for future testing an analysis, their samples will be labelled using anonymous codes. Results of any genetic tests will not be disclosed to anybody not involved with the study, in particular not to immediate relatives without prior consent of the patient.

This confidentiality will be in accordance to the recently instated EU Data protection Law (Regulation (EU) 2016/679).

# **17 ETHICAL CONSIDERATIONS**

## **17.1 Basic principles**

This study will be performed in accordance with the protocol, the principles laid down in the ICH harmonized tripartite guideline regarding GCP (Consolidated Guideline E6, July 2002), the Declaration of Helsinki (Sixth Revision, October 2008), as well as any other applicable national and international regulatory guidelines.

## 17.2 Involvement of ethical committees

The protocol and the informed consent document to be used in this study must be submitted to the Investigator's Ethics Review Committee/IRB, regulatory authority, and the sponsor IRB for approval. Written documentation of approval of both, the protocol and the informed consent, must be provided to the sponsor before starting the study.

The Investigator will ensure that the purpose of the study is explained to the patient and that written consent is obtained prior to participation in the study. The patient and the Investigator or his/her delegate will sign the consent prior to entry into the study.

The Investigator will promptly report to the Ethics Committee/IRB of all changes in the research activity and all unanticipated problems involving risks to human participants or others and will not make changes in the research without Ethics Committee/IRB approval, except where necessary to eliminate apparent immediate hazards to human participants.

## **17.3 Regulatory authorities**

The Regulatory Authorities will receive the protocol, amendments, reports on SAEs and Serious Unexpected Adverse Drug Reactions (SUSARs), and the Integrated Clinical Trial Report according

to national regulations. Written approval will be obtained from the Regulatory Authorities prior to commencement of the trial.

#### 17.4 Investigators view of the ethical issues and considerations

The investigator(s) participating in this trial, as listed above, have had the opportunity to review the protocol outline. Their concerns and suggestions have been included into the final protocol.

## **17.5 Falsification of data**

Any proven evidence of falsification of data will be dealt with in accordance with the policy of the sponsor and appropriate action will be taken.

## **18 ADMINISTRATIVE CONSIDERATIONS**

#### **18.1** Trial committees

#### 18.1.1 Trial Oversight: Trial Steering Committee (TSC)

The role of the Trial Steering Committee (TSC) is to provide overall supervision of the trial and ensure that the trial is conducted in accordance with GCP and GCLP principles. The Trial Steering Committee will formally report to the Sponsor. TSC specifics will be detailed and justified in the TSC charter. The TSC will at least consist of a sponsor representative person, the sponsor medical expert, the trial statistician, and a principal investigator (PI).

#### 18.1.2 Data Safety Management Board (DSMB)

To include an element of expert advice that is independent of the PIs and the sponsor, an independent Data Safety Monitoring Board (DSMB) will be installed. The DSMB will safeguard the interests of trial participants. The DSMB will review data and will make recommendations to the TSC regarding stopping of certain arms, or the whole trial if trial participation is an undue risk to participants and will use the safety review guidelines in their consideration. The DSMB are not executive, any decision regarding early termination of arms or the whole trial will be made by the TSC and sponsor. A DSMB charter will be established that describes the roles and responsibilities of this independent committee for the trial.

#### **18.2** Trial registration

Before study start, the trial will be registered in clinicaltrials.gov, a WHO recognized clinical trials registry.

In addition, the trial will be registered in the South African National Clinical Trials Registry.

## 18.3 Financing

The study sponsor is LegoChem Biosciences, Inc. The trial is conducted under the umbrella of PanACEA, the PanAfrican Consortium for the Evaluation of anti-TB Antibiotics. PanACEA is a not-for-profit consortium with the goal of shortening the treatment regimen of drug-sensitive TB.

LegoChem Biosciences ensures that sufficient funding of this study is available.

LegoChem Biosciences, Inc. will contribute sufficient DZD 400mg tablets Biosciences to ensure conduct of this study.

## **18.4** Patient insurance

The sponsor certifies that it has obtained or will obtain clinical trial insurance in line with the requirements in each country prior to study start. The insurance does not relieve the investigators of the obligation to maintain their own liability insurance as required by applicable law. The sponsor does not assume any obligation for the medical treatment of other injuries and illnesses.

#### 18.5 Patient compensation for trial-related expenditures

Trial participants will receive a flat sum per trial visit (and per day spent in hospital) for out of pocket expenses, which covers loss of salary, travel to/from site and other miscellaneous cost, depending on the vote of the trial sites' ethics committee. This sum will be laid down in the sites' informed consent documents to follow local practice and be approved by sites' ethics committees.

Should a trial participant have higher travelling expenses, these can be reimbursed at the discretion of the investigator. In such cases, receipts and considerations should be documented in the participant's records.

Since these payments are reimbursements of estimated cost, they do not constitute an undue incentive for trial participation.

## **18.6 Publication Policy**

After completion of the study, the data may be considered for reporting at a scientific conference and/or publication in scientific journals. LMU will be responsible for these activities and will collaborate with the investigators to determine how the manuscript is written and edited, the number and order of authors, the journal to which it will be submitted and other related issues.

The results of the study will be published independent of the outcome - positive or negative - of the study.

Under certain circumstances, i.e. when the publication of particular findings (of an epidemiological, sociological or genetics study) may present a risk to the interest of a community or population or a racially or ethnically defined group of people, it may be considered inappropriate to publish findings.

## 18.7 Protocol amendment policy

Any change to the protocol will be made by means of a protocol amendment. Any changes which affect participant safety or welfare will be submitted to the IEC/IRB and regulatory authorities prior to implementation. The Investigator, IEC/IRB, and sponsor must agree on all amendments. No amendment will be implemented until approved by the relevant authorities and signed by all required parties. Exceptions to this are when the Investigator considers that the participant's safety is compromised.

Protocol amendments detailing minor administrative changes should be submitted by the Investigator to the IEC/IRB for notification purposes as appropriate.

Protocol No: PanACEA - DECODE – 01/ LCB01-0371-20-2-02 Protocol Version No: V2.1, dated 08 September 2021

#### 20 APPENDIX

#### **20.1** Management and classification of liver toxicity

Since treatments in this study do not include standard of care for DS-TB, we decided to recommend testing for and management of drug-induced liver injury (DILI) following the FDA's guidance that provides a synthesis of patient protection considerations, and adequate characterisation of the treatment regimen's risk for DILI [66], rather than follow TB-specific guidelines.

#### 20.1.1 Prevention: Participant awareness

Remind the participant to avoid substances with the potential to cause liver damage: including alcohol and other medications such as paracetamol.

The participant must be informed about signs that might indicate worsening abnormalities or evidence of drug reaction (e.g. loss of appetite, fever, nausea, vomiting, rash, jaundice) and know to present emergently should any of these be noticed.

#### 20.1.2 Closer observation: AST/ALT > 3xULN

It is critical to initiate close observation immediately upon detection and confirmation of early signals of possible DILI, and not to wait until the next scheduled visit or monitoring interval.

A threshold of aminotransferase levels greater than 3xULN is recommended for closer observations, as lesser elevations are common and nonspecific, **if participant is asymptomatic regarding clinical signs of DILI AND bilirubin AND INR are not elevated.** 

Other laboratory findings that do not meet these criteria but raise the investigator's concern should be discussed with the sponsor medical expert.

If additional testing, beyond that specified in the trial protocol, is carried out, it is important that the subject's information be added to the CRFs and database.

Close observation includes:

- Repeating liver enzyme, serum bilirubin tests and coagulation tests two or three times weekly. Frequency of retesting can decrease to once a week or less if abnormalities stabilize or the trial drug has been discontinued and the subject is asymptomatic.
- Obtaining a more detailed history of symptoms and prior or concurrent diseases.

- Obtaining a history of concomitant drug use (including non-prescription medications and herbal and dietary supplement preparations), but especially alcohol use, recreational drug use, and special diets.
- Ruling out acute viral hepatitis types A, B, C, D, and E; hypoxic/ischemic hepatopathy as much as possible; and biliary tract disease. Ultrasound should be performed for the latter.
- Obtaining a history of exposure to environmental chemical agents.
- Obtaining additional tests to evaluate liver function, as appropriate (e.g., INR, direct bilirubin).

#### 20.1.3 Pausing treatment

Pausing of study treatment should be considered if:

- ALT or AST >8xULN
- ALT or AST >5xULN for more than 2 weeks
- ALT or AST >3xULN and (TBL >2xULN or INR >1.5)
- ALT or AST >3xULN with the appearance of fatigue, nausea, vomiting, right upper quadrant pain or tenderness, fever, rash, and/or eosinophilia (>5%)
- 20.1.4 Re-challenge with study treatment:
  - As soon as symptoms resolve and elevated ALT/AST are below 2x ULN, reintroduction of study treatment is to be discussed with the sponsor medical expert. Study treatment will be reintroduced (all drugs simultaneously). Close, biweekly monitoring of symptoms and laboratory parameters is then needed to identify repeated DILI. Should this occur, the study regimen will be permanently stopped and the participant be continued on a regimen that is considered non-toxic.
  - Inform the participant: The participant must be informed about signs that might indicate worsening abnormalities or evidence of drug reaction (e.g. loss of appetite, fever, nausea, vomiting, rash, jaundice) and know to present emergently should any of these be noticed.
  - The participant must be informed on avoiding alcohol and other liver toxic comedications or drugs.

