# 13.10 Additional safety considerations: individual patient stopping criteria for safety

• Hepatotoxicity stopping criteria: these follow the FDA guidance on evaluation of druginduced liver injury [66]. More detail on patient management in case of liver toxicity including intensifying the assessment schedule, is provided under 20.1, page 93.

A patient should discontinue study drug if:

- ALT or AST >8xULN
- ALT or AST >5xULN for more than 2 weeks
- ALT or AST >3xULN and (total bilirubin (TBL) >2xULN or INR >1.5

- ALT or AST >3xULN with the appearance of fatigue, nausea, vomiting, right upper quadrant pain or tenderness, fever, rash, and/or eosinophilia (>5%)
- As soon as symptoms resolve and elevated ALT/AST are below 2x ULN, reintroduction of study treatment is to be discussed with the sponsor medical expert. Study treatment will be reintroduced (all drugs simultaneously). Close, at least biweekly monitoring of symptoms and laboratory parameters is needed to identify repeated DILI. Should this occur, the study regimen will be permanently stopped and the participant be continued on a regimen that is considered non-toxic.
- All participants who discontinue study treatment should be followed up as described for follow-up of adverse events classified as "severe" (grade 3 and above).
- ECG stopping criterion: Participants will stop treatment if their on-treatment ECG shows a prolongation of the Fridericia corrected QT interval (QTcF) on average in triplicate ECGs to grade 3 as defined under 14.6.

In this case, the patient will be hospitalized and monitored closely with at least daily ECGs until the abnormality abates. Study drugs and other potentially offending drugs will be withheld. Blood electrolytes (mainly Mg+, Ca++, K+) will be measured and abnormalities corrected, after discussion with the sponsor medical expert.

As soon as the AE improves to grade 2 or less, study drugs might be restarted in close discussion with the sponsor medical expert, unless QTcF prolongation resulted in dangerous arrhythmias (grade 4 QTcF prolongation as defined under 14.6 *Table 2* – in this case, the patient will be discontinued from study treatment..

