#### 20.1.5 Follow-up of liver toxicities

• All participants who discontinue study treatment should be followed up as described for follow-up of adverse events classified as "severe" (grade 3 and above).

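### Protocol 20.1.3 makes stopping optional at the same four ALT/AST criteria where Protocol 13.10 directs it, and neither section says which governs

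*Protocol*

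**What the plan says.** Protocol 13.10 sets out when an individual patient stops treatment for safety. Its hepatotoxicity entry gives four ALT/AST criteria under "A patient should discontinue study drug if". For further handling it points to the appendix: "More detail on patient management in case of liver toxicity including intensifying the assessment schedule, is provided under 20.1, page 93".

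Appendix 20.1 covers management and classification of liver toxicity. Within it, 20.1.3 repeats the four criteria under "Pausing of study treatment should be considered if". Section 20.1.4 then deals with restarting: once symptoms have resolved and ALT/AST are below 2xULN, "reintroduction of study treatment is to be discussed with the sponsor medical expert". Section 20.1.5 deals with what follows a stop: "All participants who discontinue study treatment should be followed up", in the manner used for severe adverse events.

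SAP 7.3 provides for tabulating participants who discontinue because they met the stopping criteria, and names Protocol 13.10 as their source.

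**The concern.** A hepatotoxicity stopping rule should give one instruction for one laboratory result. Here it gives two. An investigator working from 20.1.3 can consider a pause, decide against it and continue dosing without departing from the appendix, although the patient has met a stopping criterion in 13.10. Section 13.10 itself sends the investigator to that appendix.

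What is at stake is patient safety and consistent handling between sites. According to Protocol 6.1.4, delpazolid had been given to humans for at most 21 days, and abnormal liver function was among the events in the 21-day study. This trial gives it for 16 weeks, and SAP 4.2 lists seven activated sites. Two sites could treat the same result differently and each cite the protocol. There is also a reporting consequence. Protocol 14.3 asks for immediate reporting of a toxicity that leads to a planned deviation from study medication. A pause would fall under that clause; continued dosing would not, although other reporting rules might still apply.

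**Working it through.** No figure in the plan depends on this, so the check is a comparison of texts.

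**Step 1: are the criteria the same?**

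| Criterion | Protocol 13.10 | Protocol 20.1.3 | Match |
|---|---|---|---|
| 1 | ALT/AST above 8xULN | above 8xULN | yes |
| 2 | ALT/AST above 5xULN, lasting over 2 weeks | above 5xULN, lasting over 2 weeks | yes |
| 3 | ALT/AST above 3xULN, plus bilirubin above 2xULN or INR above 1.5 | same | yes |
| 4 | ALT/AST above 3xULN, plus listed symptoms, rash or eosinophilia above 5% | same | yes |

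Four of four match. The only difference in wording is that 13.10 spells out total bilirubin in criterion 3.

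**Step 2: is the action the same?** No. Section 13.10 directs the stop: "A patient should discontinue study drug if". Section 20.1.3 leaves it open: "Pausing of study treatment should be considered if". The verbs discontinue and pause matter less than they seem to, because 13.10 also provides for reintroduction, in nearly the same terms as 20.1.4. The difference of substance is that one text directs and the other asks for consideration.

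**Step 3: does any text settle which governs?** No sentence states precedence. The pointer in 13.10 describes the appendix as adding detail on management and does not say that 13.10 overrides it.

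**Step 4: which rule is intended?** Three things point to 13.10. Its heading calls its contents stopping criteria. SAP 7.3 uses 13.10, and not 20.1, as the source of the stopping criteria. The ECG and neuropathy entries in 13.10 say that participants will stop, so the section as a whole is written as directions to stop.

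**Step 5: does the rest of 20.1 repair the lead-in?** Sections 20.1.4 and 20.1.5 describe restarting and follow-up, so they presuppose that treatment has stopped. They do not direct it to stop. The optional wording in 20.1.3 therefore stands for all four criteria alike.

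**Step 6: which drugs are meant?** Section 13.10 speaks of study drug and 20.1.3 of study treatment. Both re-challenge texts reintroduce all drugs at once. Where 13.10 means delpazolid alone, as for neuropathy, it says so. The liver criteria are best read as applying to the whole regimen.

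**The case against.** The best defence is that the hierarchy is clear from structure. Section 13.10 is the stopping section and 20.1 is an appendix offering more detail. Section 13.10 is also complete in itself: it gives the criteria, the condition for restarting and the follow-up. An investigator who reaches 20.1 through the pointer in 13.10 has just read the directed stop, and to continue dosing would be to disregard it. Both texts use should, the discontinuation in 13.10 is reversible, and 20.1.4 and 20.1.5 assume that a stop has occurred.

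Most of this stands, and it limits the size of the problem. A careful reader of both sections would probably stop treatment. It does not remove the mismatch. The appendix repeats the full list of criteria, so it can be used on its own, and when used that way it makes the stop optional.

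A reader might be tempted to go further and infer that 20.1.2 opens an observation route that permits dosing above a stopping threshold. That section calls for closer observation above 3xULN "if participant is asymptomatic regarding clinical signs of DILI AND bilirubin AND INR are not elevated", with no upper ALT/AST limit, and allows that "Frequency of retesting can decrease to once a week or less if abnormalities stabilize or the trial drug has been discontinued". On that reading criteria 1 and 2 would be worse affected than the other two. The documents do not support this. Section 20.1.2 says when extra monitoring begins; it does not say whether dosing continues, and its tests apply to patients on or off drug. The retesting sentence goes on to require that the subject be asymptomatic. Once a patient reaches "ALT or AST >8xULN", 20.1.3 applies as well. Section 20.1.2 adds nothing to the conflict.

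**Conclusion.** The inconsistency is real and should be corrected. For four of four hepatotoxicity criteria, Protocol 13.10 directs a stop and Protocol 20.1.3 makes it optional, with no statement of which governs. The cause is the 20.1.3 lead-in alone.

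The size is modest. The stronger text says should, not must, and its discontinuation can be followed by re-challenge. The documents give no incidence for the four criteria, so the number of patients affected cannot be estimated, and no effect on endpoint counts is claimed. The conclusion that 13.10 is the intended rule rests on its heading and on SAP 7.3, not on any explicit statement. The mismatch in wording is certain. That a patient would in fact be dosed through a criterion is only a possibility that the wording leaves open.

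**What to change.** Change the lead-in of Protocol 20.1.3 to: *Study treatment (all study drugs) should be discontinued, as required by 13.10, which governs, with re-challenge only as described in 13.10 and 20.1.4, if:*. Alternatively, delete the list in 20.1.3 and refer to 13.10, so that the criteria stand in one place only.

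The cost is one line of protocol text. Assessments, data collection, sample size and the SAP are unchanged.
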